119 days. Bode and colleagues studied the safety and efficacy of Novolog insulin in 19
120 subjects used the same infusion set tubing for 7 days and overall, no negative effects
121 on glycemic control were observed during this period but it was noted that serum
122 glucose levels began to increase the longer the infusion set was used [17]. There have
123 been three published randomized trials assessing length of infusion set wear beyond 3
124 days. One study compared using insulin lispro to insulin aspart for 5 days of infusion set
125 wear [18]. There was no difference between the two insulins, with an average length of
126 infusion set wear of 98 and 96 hours, respectively. The researchers reported increased
127 glucose levels after 48 hours of wearing an infusion set and recommended changing
128 infusion sets every 2 days. We conducted a randomized, open-label, crossover study of
129 20 subjects who wore Teflon catheter (Quick-Set) and steel catheter (Sure-T) infusions
130 set for 38 weeks and 39 weeks respectively with no difference in the survival curves of
131 the infusion sets. The mean duration of wear was 5.5 days with a standard deviation of
132 1.9 days. Intersubject variation and the majority of failures were secondary to
133 uncorrectable hyperglycemia which indicates insulin flow occlusions [19]. Another
134 multicenter, crossover trial showed no difference in infusion set survival or mean
135 glucose in 20 type 1 diabetes subjects wearing the sets in either lipohypertrophied and
136 nonlipohypertrophied tissue [20].
137

138 **Etiology of Infusion Set Failures**

139 The underlying cause of intersubject variation in infusion set wear time is unknown but
140 in the prior infusion set studies time to failure was primarily associated with
141 hyperglycemia which did not improve with correction dose of insulin. In most of these
142 subjects, there was no overt back-pressure error from the pump. "Silent occlusions"
143 would be the most likely causative factor, and the additional slitted openings would
144 reduce the risk of silent occlusions and subsequent hyperglycemia (**Figure 2**). The
145 Lantern is designed to reduce failures due to kinking. Other less common causes for
146 set failure would probably not be affected by the Lantern; these include 10-15% being
147 pulled out by accident (tubing caught on a door handle for example), 6-12% from loss of
148 adhesiveness, 5-13% removed for pain and 5-10% for erythema/induration concerning

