149 for infection. Approximately 30% of subjects reporting erythema/induration also
150 reported pain [19-20, unpublished data]. In addition, this will be the first infusion set
151 study to assess attitudes towards diabetes technology, which could also correlate with
152 time to failure and explain some of the intersubject variability.

[figure not shown]

153
154 **Figure 2.** Lantern catheter being kinked by underlying muscle, but insulin continues to be delivered
155 through side openings.

156

157 **Preliminary Data**

158 The single use infusion set is similar to the already CE approved Inset II infusion set
159 with the addition of below features, and consists of an insertion device with introducer
160 needle that inserts the soft cannula into the skin. The intervention infusion set presents
161 a hydrophilic coated soft cannula with Lantern Technology – 6 slits (**Figure 3**).
162

163
164 **Figure 3.** Lantern catheter (left) demonstration of increased surface area (middle) and μ CT
165 reconstruction of insulin delivery from an occluded catheter in human skin explant (right).

166

167

168 Materials in fluid paths has been tested with insulin lispro, aspart, glulisine and regular
169 human insulin. A swine study conducted at the Medical University of Graz compared
170 the immune response to insulin infusion systems of different materials over a course of
171 7 days of wear time in 10 female farm swine. The manufacturer analyzed the
172 inflammatory response to 2 commercially available catheters (Teflon and steel) and 3
173 Teflon prototypes that were implanted into the subcutaneous adipose tissue for 1 day, 4
174 days and 7 days. Two of the three prototypes were coated with passive coatings, which
175 suppress the inflammatory response without releasing an anti-inflammatory agent. The
176 third prototype was a new all-in-one catheter design (blinded for investigator) that did
177 not require a separate inserter. The impact of an anti-inflammatory passive coatings on
178 the foreign body response was evaluated. All catheters were tested for a wear time of 1

179 day, 4 days and 7 days. Tissue was explanted and immune cells and connective tissue
180 were stained using standard histopathological methods. This study indicated potential
181 beneficial effects of passive anti-inflammatory coatings for insulin infusion catheters.
182

183 Another study conducted at the Joanneum Research Institute, Graz assessed the

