184 insulin distribution in subcutaneous adipose tissue when using infusion set with Lantern
185 Technology. The infusion set was inserted into fresh human adipose tissue explants
186 with the aim to investigate the effect of catheter designs on the formation of
187 subcutaneous insulin depots. The study showed that the full functionality of the novel
188 insulin catheter is guaranteed independent of whether the catheter is open, kinked or
189 distally occluded. Therefore, it is not necessary to replace a kinked catheter or a
190 catheter with a clogged tip from the viewpoint of proper insulin delivery, which reduces
191 the incidence of unexplained hyperglycemia and even ketoacidosis which can be
192 associated with infusion set failures, as well as decreasing the discomfort for patients of
193 inserting multiple infusion catheters as a result of early failure. Study investigators
194 concluded that the new infusion catheter can provide a valuable contribution to patients'
195 well-being and safety.
196

197 In data that will be presented at the American Diabetes Association 2018 meeting,
198 glucose clamp studies were conducted in Graz among 16 patients with type 1 diabetes
199 (age 44.2 ± 15.4 years, BMI 24.5 ± 2.3 kg/m 2 , HbA1c 55 ± 8 mmol/mol, diabetes
200 duration 20 ± 9 years) with type 1 diabetes. All 16 patients wore the set for 7 days
201 without severe hypoglycemia or diabetic ketoacidosis. Geometric means of maximum
202 glucose infusion rates were comparable for days 1, 4 and 7. This preliminary data
203 strongly supports the safety of this infusion set and the need for real world testing of
204 longevity.
205

206 **Protocol Synopsis**

207 Part 1: Pilot Safety and Extended Wear Tolerability Study

208 This is a pilot study to obtain preliminary data upon which to base the length of wear for
209 the second part of the study. The study is not intended for registration purposes or to
210 support a 510(k) submission. The study will be conducted at one site: Stanford
211 University.
212

213 This study will enroll 24 subjects to establish the maximum length of Lantern infusion
214 set wear when 80% of sets are still functional (excluding accidental "pull-outs"). We will
215 plan for a staged enrollment, the first 10 subjects will be 18 or older. If there are no
216 untoward effects we will begin enrolling participants age 15-18. Each participant will
217 place the set and wear it for 10 days or until set failure and data will be collected on the

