218 cause of set failure. If a set is accidentally pulled out, it can be replaced by the subject.
219 Subjects will either complete a daily online questionnaire or they will be contacted daily
220 by research staff to determine if a set has failed, the cause of failure, and to record
221 measured erythema and edema at a failed infusion site. Failures are based on:
222

- 223 1. Presence of serum ketones with hyperglycemia
- 224 2. Unexplained hyperglycemia
3. Signs of infection at the infusion site

225 4. Pump occlusion alarm
226 5. Adhesive failure

227
228 Since infusion set failures will occur after variable lengths of wear, regularly scheduled
229 visits are unlikely to capture the day of an infusion set failure. Instead the subject will be
230 taught how to insert the set, measure erythema and induration with a ruler marked in
231 millimeters and to take a picture of the infusion site. Subjects will be instructed to text
232 the study team when they remove their infusion set and to send a picture of the infusion
233 site and measurements. If there is any evidence of an infection (≥ 10 mm of erythema or
234 induration), they will be asked to come in that day for an unscheduled visit.

[figure not shown]
235
236 Part 2: Extended Wear Randomized Controlled Crossover Study

237 This will be a masked, randomized controlled crossover study at Stanford University
238 (**Figure 4**). The study is intended for registration purposes and to support a 510(k)
239 submission. The planned duration of wear and visit schedule will be determined by the
240 results of Part 1. Participants, age 15 and over, will be randomized to wear the masked
241 investigational or control infusion set first. The control set is the Mio (used with
242 Medtronic pumps) or Inset II (used with other pump models) which are the precursors to
243 the Convatec Lantern and do not contain slits. Each participant will wear both the
244 investigational and control infusion set. Subjects will act as their own control.

245
246 At home subjects will examine their infusion site when they are changing an infusion set
247 and assess for signs of bleeding, local tissue reaction or infection. They will record
248 redness, induration, and bruising in mm, and call one of the investigators if there is
249 more than 10 mm of erythema or induration. They will be given a ruler for making these
250 measurements. If there is more than 3 mm of induration or redness they will be asked to

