474 labeling. While the G6 system is FDA approved for non-adjunctive use without
475 calibration, we will ask patients to confirm blood glucose with glucometer prior to
476 removing an infusion set. Subjects will be instructed to check blood ketones using a
477 blood ketone meter if there is unexplained hyperglycemia. Unexplained hyperglycemia
478 refers to high glucose levels outside of the usual times they may occur, such as in the
479 initial few hours following a meal. If the CGM stops functioning during the study, the
480 subjects will insert a new sensor which will be provided to them. If there is an
481 accidental removal of an infusion set the participant will have access to a replacement
482 which he or she will be taught to place.
483

484 *Determination of an infusion set failure:*

485 They will be instructed to replace the infusion set, in the following situations.

- 486 1. The presence of serum ketones >0.6 mmol/L with meter glucose >250 mg/dL, in
487 the absence of illness, vigorous fat burning exercise, starvation or alcohol.
- 488 2. Unexplained hyperglycemia, >250 mg/dL, outside anticipated periods of
489 carbohydrate consumption, illness, missed insulin doses and menstruation. This
490 hyperglycemia cannot be reduced with appropriate correction doses of insulin
491 (such as a decrease of at least 50 mg/dL in 1 hour following a correction dose).
- 492 3. Signs of infection at the infusion site including pain, erythema or induration >10
493 mm in diameter.
- 494 4. Pump occlusion alarm
- 495 5. Adhesive failure (only the adhesive on the infusion set will be used)

496
497 *Recording of infusion site information:* At home they will exam their infusion site each
498 day for signs of redness and/or induration. If they detect redness or induration they will
499 record them in mm and send a text to study staff. At the time an infusion set is removed
500 they will record redness and induration in millimeters, and call one of the investigators if
501 there is more than 10 millimeters of erythema or induration. They will be given a ruler
502 for making these measurements. Subjects will record the time and date that infusion
503 sets or sensors are removed, and document why they removed the set and take a
504 picture of the infusion site after the infusion set is removed if there is ≥ 3 mm of

505 induration or erythema. The picture and infusion site measurements will be sent via text

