743 Before beginning a larger cross-over study we would perform this pilot study to
744 determine the maximum length of Lantern infusion set wear when 80% are still
745 functional if failure was not due the infusion set being accidentally pulled out. This study
746 is not statistically powered.

747

748 **Part 2**

749 Primary Outcome

750 Our primary outcome will be time to failure of each infusion set. We have reviewed 353
751 weeks of infusion set wear from prior studies [19-20, unpublished data] and subjects
752 who wear the control set have an average length of wear of 5.1 days with a standard
753 deviation of 1.7 days and intra-subject correlation of 0.69. For a meaningful clinical
754 benefit, the subjects who wear the treatment set should extend wear by at least 1 day to
755 an average length of wear of 6.1 days. A sample size of 40 subjects will provide 95%
756 power to detect a difference of 1 day in the average length of wear in a two-sided test
757 with an alpha level of 0.05. A minimum of 25 subjects must be recruited for 80% power.

758

759 Exploratory Outcomes

760 Other outcomes will include – BMI, cause of infusion set failure, measurements of
761 erythema and induration, pump insulin delivery data, glucometer readings, ketone meter
762 data, average daily CGM blood glucose, DSAT/DDS score and infusion set
763 questionnaire.

764

765 We will summarize the other secondary measures using means, standard deviation,
766 medians, ranges, proportions and 95% confidence interval, as appropriate. We will also
767 explore the relationship between BMI, DSAT/DDS score and the time to failure primary
768 outcome. Finally, we will test if there is a significant change in the DSAT/DDS score
769 following participation in the clinical trial.

770 **CHAPTER 7: References**

1. The Diabetes Control and Complications Trial Research Group. "The effect of intensive treatment of diabetes on the development and progression of long-term complications in insulin-dependent diabetes mellitus. The Diabetes Control and Complications Trial Research Group." *N Engl J Med.* 1993 Sep 30;329(14):977-86.
2. Diabetes Control and Complications Trial/Epidemiology of Diabetes Interventions and Complications (DCCT/EDIC) Study Research Group. "Intensive diabetes treatment and cardiovascular disease in patients with type 1 diabetes." *N Engl J Med.* 2005 Dec 22;353(25):2643-53.

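### Does Part 2 need a rule for accidentally pulled-out sets, given that the documents call them failures in one place and leave them out in others?

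*Combined protocol and SAP*

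**What the plan says.** - **Chapter 1, Etiology of Infusion Set Failures.** Among the less common causes, it says that "set failure would probably not be affected by the Lantern; these include 10-15% being" "pulled out by accident (tubing caught on a door handle for example". Loss of adhesiveness is listed separately, at 6-12%. The source given at the end of the list is "reported pain [19-20, unpublished data".
- **Chapter 6, Part 2, Primary Outcome.** The outcome is time to failure of each set. The planning figures (control mean 5.1 days, SD 1.7, intra-subject correlation 0.69) come from 353 "weeks of infusion set wear from prior studies [19-20, unpublished data] and subjects". No rule on pull-outs is attached.
- **Part 1.** The Protocol Synopsis seeks the longest "set wear when 80% of sets are still functional (excluding accidental" pull-outs. Chapter 6, Part 1 has the same exclusion: "functional if failure was not due the infusion set being accidentally pulled out". The synopsis adds: "If a set is accidentally pulled out, it can be replaced by the subject".
- **Part 2, Chapter 3, Home Monitoring.** After "accidental removal of an infusion set the participant will have access to a replacement". The five failure criteria then follow under their own heading: ketones with hyperglycemia, unexplained hyperglycemia, signs of infection, occlusion alarm and adhesive failure. Pull-out is not among them.
- **Part 2, Chapter 3, Initiation visit.** A set that fails within 24 hours is replaced with the assigned study set. After a later failure the subject goes back to the usual set.

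**The concern.** A pull-out seems to have three statuses: a cause of failure in the background, an excluded failure in Part 1, and an event absent from the list in Part 2. If it is a failure in Part 2, the subject should return to the usual set after 24 hours, yet Home Monitoring offers a replacement with no time limit. If it is not a failure, the Part 2 endpoint may differ from the one behind the 5.1-day planning mean, because the pull-out rate and that mean share a citation.

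At 10-15% of sets, the choice could affect the size of the primary difference and the power, in a study meant to support a 510(k) submission. A choice made after seeing results would also invite criticism.

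**Working it through.** **1. The passages side by side**

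| Place | Status of a pull-out |
|---|---|
| Chapter 1, Etiology (background) | a cause of set failure in earlier studies |
| Synopsis and Chapter 6, Part 1 | excluded from the 80% target |
| Synopsis and Chapter 3, Part 2 criteria | not listed |
| Chapter 3, Part 2, Home Monitoring | handled apart from failures, replacement offered |
| Chapter 6, Part 2 | silent |

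The Part 1 and Part 2 rows point the same way. If a pull-out is not a failure, the return-to-usual-set rule is never triggered by one, so the Initiation visit and Home Monitoring texts do not conflict. Only the background paragraph stands apart, and it does not define the Part 2 endpoint.

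**2. The plan's own power figure**

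Paired t-test, two-sided alpha 0.05, noncentrality = difference × √N / SD_d, with SD_d = 1.7 × √(2(1 − r)).

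- SD_d = 1.7 (equivalent to r = 0.5): noncentrality √40/1.7 = 3.72, power 95.2% at N = 40; 5/1.7 = 2.94, power 80.6% at N = 25. This reproduces the stated 95% and 80%.
- r = 0.69: SD_d = 1.7 × √0.62 = 1.339, power 99.6% and 94.8%. The stated correlation therefore seems not to have been used. That is a separate matter, and on the plan's own inputs it errs towards more subjects.

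**3. How many sets are involved**

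Assumptions: normal failure times with means 5.1 and 6.1 and SD 1.7; a constant pull-out rate, equal in both arms; 10-15% read as the share of control sets pulled out before failing. The rate λ solves mean[1 − exp(−λ × failure time)] = 0.10 or 0.15, giving 0.0208 or 0.0321 per day. Of 80 sets, about 9 to 13 are pulled out at a 10-day limit and 7 to 10 at 4.6 days. The 4.6 days is the average time of the fifth failure among 24 Lantern sets with mean 6.1, when 19/24 = 79% are left.

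**4. Effect on the mean difference**

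Observed time = min(failure, limit), or min(failure, pull-out, limit) if pull-outs count.

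| Limit | Pull-outs ignored | Counted, 10% | Counted, 15% |
|---|---|---|---|
| 10 days | 0.99 | 0.89 | 0.83 |
| 4.6 days | 0.28 | 0.26 | 0.25 |

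Moving the limit from 10 to 4.6 days costs 0.71 day. Counting pull-outs costs at most 0.16.

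**5. Effect on power at N = 40, 10-day limit**

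- *Pull-out not a failure, clock restarted on the replacement:* unchanged, 95% with SD_d 1.7 or 99.6% with 1.339.
- *Censored at pull-out, log-rank with subject-robust variance:* 96% without pull-outs, then 90-95% (10%) or 88-93% (15%).
- *Counted, planning figures taken to include pull-outs:* with SD_d 1.339, noncentrality 0.89 × 6.32/1.339 = 4.20 and 0.83 × 6.32/1.339 = 3.92, power 98% and 97%. With SD_d 1.7 the noncentralities are 3.31 and 3.09, power 90% and 85%.
- *Counted, with pull-outs added on top of SD 1.7 and r 0.69:* paired-t power 76% (10%) or 62% (15%) if pull-outs are independent within a subject, and about 99% if fully shared. In the independent case the observed control SD would be 1.84 or 1.90 and the correlation 0.43 or 0.35. Those are not the plan's 1.7 and 0.69.

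**6. Direction**

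With equal pull-out rates and no true difference between sets, the expected difference is zero under every rule. With a true gain, counting pull-outs only dilutes it.

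**The case for a change.** The strongest case is that even on the natural reading a rule is missing. Non-failure does not tell the analyst whether to censor, restart the clock or use the replacement's time. Chapter 6 words a pull-out in Part 1 as a failure that needs an explicit exclusion, and Part 2 has none. If the wear limit turns out short, the range is also wide: at 4.6 days log-rank power is 77% without pull-outs, 67-73% with censoring, and 41-73% if they are counted.

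The first part stands: the detail is absent. The rest weakens on inspection.

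- The low ends need three things together: planning data without pull-outs, a Part 2 analysis that counts them against its own list, and independence within a subject.
- The mismatch with the planning data rests on a shared citation alone. The documents do not say whether 5.1 and 1.7 days count pull-outs, or whether 10-15% is a share of sets or of failures.
- At 4.6 days most of the lost difference comes from the limit, whichever rule is used.
- Neither obvious rule is better outright. Censoring assumes that a pull-out is unrelated to a coming failure, which is doubtful for a loosening set. Time to removal for any cause avoids that assumption but mixes in events the Lantern is not expected to alter.

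**Conclusion.** The point does not call for a change. The Part 2 criteria, the separate handling of accidental removal and the Part 1 exclusion all support treating a pull-out as a non-failure, and on that reading the Part 2 passages agree. What remains is a gap in analysis detail that a competent analyst can fill while the sets are still masked. Chapter 3 already has subjects record the date, time and reason of each removal, so any of the rules can be applied to the same data. The choice between censoring and counting is a fair trade-off.

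The size is modest at a 10-day limit: a true 1-day gain shows as 0.99 day, or 0.89 to 0.83 if pull-outs are counted. With the planning SD and correlation taken as stated, power stays at 97% or more; with the SD of the difference that reproduces the plan's 95%, it is 85-90%. This rests on normal wear times, 10-15% read as a share of control sets, and an equal, constant pull-out rate in both arms. Chapter 1 supports equal rates, since it expects no Lantern effect on this cause. A clear difference in pull-outs between arms would reopen the question.
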